### 14.4. Level of Statistical Significance

All *co-primary safety*, *co-primary efficacy* and *secondary* hypotheses will be tested using a multibranch gate keeping strategy. Study hypotheses will be evaluated sequentially as follows: First, co-primary safety hypotheses will be tested using 95% central posterior credible intervals for the probability of Grade or higher and unacceptable lens fitting. Both hypotheses must be met in order to test co-primary efficacy hypotheses. Since both hypotheses must pass to continue testing primary hypotheses, an overall family-wise type I error rate of 5% will be allocated to co-primary efficacy hypotheses using a Bonferroni approach. Each co-primary efficacy hypothesis will be tested using two-sided type I error rate of 1% (5 hypotheses total

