### Co-Primary Efficacy Hypotheses:

1. After approximately 1-week of wear in the optimized Test lenses, the mean overall quality of vision score of the Test lenses will be statistically better than 41 points for the myope population. This will be recorded by the subject using the CLUE Follow-up Questionnaire.
2. After approximately 1-week of wear in the optimized Test lenses, the mean overall quality of vision score for the Test lenses will be statistically better than 36 points for the hyperope population. This will be recorded by the subject using the CLUE Follow-up Questionnaire.
3. After approximately 1-week of wear in the optimized Test lenses, the mean distance, binocular, high luminance, high contrast logMAR visual acuity score of the Test lens will be statistically lower than 0.0 logMAR.
4. After approximately 1-week of wear in the optimized Test lenses, the mean intermediate, binocular, high luminance, high contrast logMAR visual acuity score of the Test lens will be statistically lower than 0.17 logMAR.
5. After approximately 1-week of wear in the optimized Test lenses, the mean near, binocular, high luminance, high contrast logMAR visual acuity score of the Test lens will be statistically lower than 0.17 logMAR.

All safety and efficacy co-primary hypotheses must be satisfied in order to meet the study objectives and to test any secondary hypotheses.

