# Clinical Study Protocol

## Johnson & Johnson Vision Care, Inc.

=5%). All co-primary safety and co-primary efficacy hypotheses must be met to test any secondary hypotheses.

*Secondary hypotheses* (except for lens fit success) will be tested with using an overall two-sided family-wise type I error rate of 5% (1% individually). Lens fit success will be tested using a 99% credible interval.

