### **Primary Efficacy Hypothesis 1:**

The null and alternative hypothesis to test for superiority of Myopes relative to the threshold 41 CLUE points are as follows:

$$H_0: \mu_{Test} \leq 41$$

$$H_A: \mu_{Test} > 41$$

Where  $\mu_{Test}$ , represents the population mean for Myopes at the 1-week follow-up with respect to CLUE vision scores. Superiority will be declared if the lower limit of the 95% CI is above 41.

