# Clinical Study Protocol

## Johnson & Johnson Vision Care, Inc.

Where  $\mu_{Test}$ , represents the population mean for Hyperopes at the 1-week follow-up with respect to CLUE vision scores. Superiority will be declared if the lower limit of the 95% CI is above 36.

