### **Primary Efficacy Hypothesis 3:**

The null and alternative hypothesis for binocular distance HLHC visual performance to test for superiority of Aurora relative to the threshold 0.0 logMAR are as follows:

$$H_o: \mu_{Test} \geq 0 \text{ logMAR}$$
$$H_A: \mu_{Test} < 0 \text{ logMAR}$$

Where  $\mu_{Test}$ , represents the population mean for Aurora at the 1-week follow-up with respect to distance HLHC visual performance. Superiority will be declared if the upper limit of the 95% CI is below 0.0.

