### **Primary Efficacy Hypotheses 4 and 5:**

The null and alternative hypothesis for binocular intermediate and near HLHC visual performance to test for superiority of Aurora relative to the threshold 0.17 logMAR are as follows:

$$H_o: \mu_{Test} \geq 0.17 \text{ logMAR}$$
$$H_A: \mu_{Test} < 0.17 \text{ logMAR}$$

Where  $\mu_{Test}$ , represents the population mean for Aurora at the 1-week follow-up with respect to HLHC visual performance. Superiority will be declared if the upper limit of the 95% CI for either intermediate or near is below 0.17.

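### With all five co-primary efficacy tests required to pass, the Bonferroni split to 1% each is unnecessary for the plan's 5% target, and it contradicts the 95% intervals that decide those tests

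*Combined protocol and SAP*

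**What the plan says.** **Level.** Section 14.4 says that "an overall family-wise type I error rate of 5% will be allocated to co-primary efficacy hypotheses using a Bonferroni" approach, and then: "Each co-primary efficacy hypothesis will be tested using two-sided type I error rate of 1% (5 hypotheses total" giving 5%. Section 14.2 sizes the efficacy tests at two-sided 1%. The bootstrap paragraphs of section 14.5 (CLUE vision and visual performance) repeat an alpha of 0.01 per test.

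**Success rule.** Section 2.3: "All safety and efficacy co-primary hypotheses must be satisfied in order to meet the study objectives and to test any secondary hypotheses". Section 14.4 repeats it: "All co-primary safety and co-primary efficacy hypotheses must be met to test any secondary hypotheses".

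**Decision rules.** Section 14.5 decides all five hypotheses by a two-sided 95% interval:
- CLUE vision, myopes: "Superiority will be declared if the lower limit of the 95% CI is above 41".
- CLUE vision, hyperopes: "Superiority will be declared if the lower limit of the 95% CI is above 36".
- Distance acuity: "Superiority will be declared if the upper limit of the 95% CI is below 0.0".
- Intermediate and near acuity: "Superiority will be declared if the upper limit of the 95% CI for either intermediate or near is below 0.17".

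**Neighbouring families.** The two safety hypotheses, which must also both pass, are each judged by a 95% credible interval with no split. The secondary CLUE tests are given 1% each in section 14.4 but are decided by 95% intervals in section 14.6.

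**The concern.** A Bonferroni split guards against the extra chances of error that arise when success on any one of several tests supports a claim. Here success requires every test, so there are no extra chances to guard against: if any one null hypothesis is true, false overall success requires rejecting that particular null. The split therefore answers a multiplicity problem that the success rule has already removed.

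What is at stake is mainly clarity. One part of the plan sets a 1% criterion for each efficacy test and another sets 5%. The same data could be called a success or a failure according to which section the analyst follows. If the 1% criterion governs, each test also needs a larger observed margin than the 5% target calls for.

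**Working it through.** **1. The plan's own figures.** Five tests at 1%: 5 × 0.01 = 0.05, as stated. Combined efficacy power: 0.99^5 = 0.951, matching the stated value of about 95%.

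**2. Study-level error when all must pass.** If null hypothesis *j* is true, P(all five reject) ≤ P(test *j* rejects) ≤ its level. No independence is needed.
- Each test at two-sided 5%: bound 5%, or 2.5% in the tested direction.
- Each test at two-sided 1%: bound 1%, or 0.5% in the tested direction.

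A simulation of five normal statistics (200,000 draws, correlation 0, 0.5 and 0.9), with one null at its boundary and four hypotheses clearly met, gave about 0.025 and 0.005.

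The chance of at least one false single rejection is a different quantity. With five independent true nulls it is 1 − (1 − 0.025)^5 = 11.9% unsplit and 1 − (1 − 0.005)^5 = 2.5% split.

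**3. Margin by which the observed mean must beat its threshold.** Half-width = t × SD/√n, with SDs from Table 7 and completers from section 4.3 (100 in all, 60 myopes, 40 hyperopes). The plan uses bootstrap intervals, so these t-based widths are approximations.

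| Endpoint | SD | n | 1% | 5% |
|---|---|---|---|---|
| Distance (logMAR) | 0.0848 | 100 | 0.022 | 0.017 |
| Intermediate (logMAR) | 0.1129 | 100 | 0.030 | 0.022 |
| Near (logMAR) | 0.1264 | 100 | 0.033 | 0.025 |
| CLUE vision, hyperopes | 17.27 | 40 | 7.4 | 5.5 |
| CLUE vision, myopes | 16.84 | 60 | 5.8 | 4.4 |

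For hyperopes, 36 + 5.5 = 41.5 and 36 + 7.4 = 43.4. An observed mean between these values passes the section 14.5 rule and fails the section 14.4 level.

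**4. Power at the planned completers.** Power = P(T > t(1−α/2, n−1)), where T is noncentral t with noncentrality (margin/SD)√n. At the Table 7 means, joint efficacy power (product of the five) is 0.99997 at 1% and 0.999999 at 5%.

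The level matters only for margins much smaller than planned. The true means below, other than the Table 7 values, are assumptions:

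| Near acuity, true mean | Power at 1% | Power at 5% |
|---|---|---|
| 0.085 (Table 7) | >99.99% | >99.99% |
| 0.11 | 98% | >99% |
| 0.12 | 91% | 97% |
| 0.13 | 70% | 88% |
| 0.14 | 40% | 65% |

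| Hyperope CLUE, true mean | Power at 1% | Power at 5% |
|---|---|---|
| 57.1 (Table 7) | >99.99% | >99.99% |
| 48 | 95% | 99% |
| 46 | 82% | 95% |
| 44 | 59% | 82% |
| 42 | 32% | 57% |

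**5. Table 8 efficacy rows at the stated n** (same formula, Table 7 means and SDs):

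| Endpoint | n | Stated | At 1% | At 5% |
|---|---|---|---|---|
| Distance | 17 | 99.4 | 98.4 | 99.9 |
| Intermediate | 11 | 99.3 | 98.3 | 99.9 |
| Near | 48 | 99.0 | 97.2 | 99.5 |
| CLUE hyperopes | 14 | 99.4 | 91.8 | 98.8 |
| CLUE myopes | 18 | 99.0 | 96.9 | 99.6 |

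At the 1% level named in section 14.2, none of the stated powers is reached. The joint value at these n is 0.984 × 0.983 × 0.972 × 0.918 × 0.969 = 0.84, against about 95% stated. The planned completers exceed every one of these n.

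**The case against.** The strongest case for the plan is that a stricter level is a legitimate conservative choice in a single-arm study judged against fixed thresholds. A reader might infer that the split achieves nothing. The documents do not support that: it lowers the study-level bound from 5% to 1%, and it would protect separate claims on single endpoints. This part of the objection stands. However, the plan states 5% as its target, gives no reason for wanting 1% overall, and provides for no separate co-primary claims.

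A reader might also infer that the split makes every efficacy test stricter and costs the study power. That holds only if section 14.4 governs; under the section 14.5 rules no test is stricter. Even at 1% the planned power is effectively complete. The means at which the level matters lie far from the plan's data: section 1.5 reports near acuity means of 0.057 to 0.091 in the earlier studies, so 0.13 would be worse than all of them.

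Finally, a reader might conclude that the split caused the clash between 1% and 95% intervals. It did not: the secondary family, where a split is appropriate, has the same clash. The comparison with the unsplit safety tests is suggestive only, because those rest on Bayesian credible intervals and not on an allocated alpha.

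**Conclusion.** The point holds as an unnecessary adjustment joined to a contradiction, and it is minor in effect. Because all five hypotheses must pass, two-sided 5% per test already meets the plan's 5% target, and the split only tightens the bound to 1%. The documents give two deciding levels for the same tests, and that must be settled whichever level is preferred.

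The conclusion rests on the all-must-pass rule of sections 2.3 and 14.4. The rule for hypotheses 4 and 5 in section 14.5 is worded so that either distance could suffice. Read literally, that undercuts the argument, so it has to be corrected in the same edit. The numerical results assume the Table 7 SDs, the planned completers and t-based intervals. The sample size does not change, because the safety endpoints set the 100 completers.

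**What to change.** 1. **Section 14.4:** delete the Bonferroni allocation for the co-primary efficacy family. State that each hypothesis is tested at two-sided 5% by its 95% interval, with success only if all five pass.
2. **Section 14.5:** remove the alpha of 0.01 from the CLUE vision and visual performance paragraphs, and require both intermediate and near acuity to be below 0.17.
3. **Sections 14.4 and 14.6:** keep 1% per test for the secondary family, which is not all-must-pass, and change the 95% confidence intervals for the secondary CLUE tests to 99%. CLUE vision then needs a 95% interval for the primary test and a 99% interval for the secondary one, both from the same bootstrap. Lens fit success shows a similar discrepancy (99% credible interval in section 14.4, 95% in section 14.6) and should be reconciled too.
4. **Section 14.2 and Table 8:** change the efficacy level in the text and restate the powers. At two-sided 5% and the stated n they are 99.9, 99.9, 99.5, 98.8 and 99.6%. Hyperope CLUE needs 15 rather than 14 for 99%, well below the 40 planned.

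If the sponsor does want 1% per co-primary test, the alternative is to say so with a reason, change the section 14.5 intervals to 99%, and restate Table 8 at 1% (98.4, 98.3, 97.2, 91.8 and 96.9%).

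The cost is wording only: no change to sample size or data collection, and the 5% target stays protected.

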# Clinical Study Protocol

## Johnson & Johnson Vision Care, Inc.

=5%). All co-primary safety and co-primary efficacy hypotheses must be met to test any secondary hypotheses.

*Secondary hypotheses* (except for lens fit success) will be tested with using an overall two-sided family-wise type I error rate of 5% (1% individually). Lens fit success will be tested using a 99% credible interval.

### 14.5. Primary Analysis

#### **Primary Safety Analyses:**

All primary safety analysis will be conducted on the safety population.

#### **Grade 3 or Higher SLF**

Grade 3 of Higher SLFs will be analyzed using a Bayesian beta-binomial model with correlated binary data.

#### **The Model:**

Let  $Y_1$  and  $Y_2$  denote the binary outcomes of lens fit acceptance (Yes/No) in left and right eyes, respectively, across dispensing and follow-up visits when wearing the Test lens. Considering the correlation,  $\rho$ , between  $Y_1$  and  $Y_2$ , the distribution of the sum  $Y = Y_1 + Y_2$  is obtained by the mixture of two variables. One of them follow a binomial distribution  $Bin(2, p)$  with mixing probability  $(1 - \rho)$  and the other one follows a modified Bernoulli distribution,  $MBern(p)$ , taking value 0 and 2 rather than conventional 0 and 1, with mixing probability  $\rho$ :

$$P(Y = y | p, \rho) = (1 - \rho)Bin(2, p)I_{A1} + \rho MBern(p)I_{A2},$$

where  $I_{A1} = \{0, 1, 2\}$ ,  $I_{A2} = \{0, 2\}$  and  $p$  is the probability of success (i.e., acceptable lens fitting).

To overcome the complexity of the mixture likelihood a latent variable  $Z_i, i = 1, 2$  is introduced in the model to indicate in which component of the model the observation  $y_i, i=1, 2$ , belongs to, that is,

$$Z_i = \begin{cases} 1, & \text{if the observation belong to the MBern}(p), \\ 0, & \text{if the observation belong to the Bin}(2, p) \end{cases}$$

The joint distribution of the augmented data  $(Y_i, Z_i), i = 1, 2$ , is given by

$$\begin{aligned} P(Y = y_i, Z = z_i | p, \rho) \\ = \rho^{z_i} p^{y_i z_i / 2} (1 - p)^{(2 - y_i) z_i / 2} (1 - \rho)^{1 - z_i} \binom{2}{y_i} p^{y_i (1 - z_i)} (1 - p)^{(2 - y_i) (1 - z_i)} \end{aligned}$$

The probability  $p$  links to the regression variables through a logit transformation as follow:

$$\text{logit}(p) = \beta_0 + \beta_1 \text{lens}$$

It is assumed that  $\beta_0, \beta_1$  and  $\rho$  to be independent with a non-informative prior  $N(0, 1000)$  for  $\beta_0$  and  $\beta_1$ , and  $\text{beta}(0.5, 0.5)$  for  $\rho$ . The Metropolis sampler algorithm as implemented in the SAS/STAT MCMC Procedure will be used to estimate the posterior distributions of the

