### **Primary Safety Hypothesis 1:**

The null and alternative hypotheses for evaluating superiority of the Test lens relative to 5% are as follows:

$$H_0: p_T \geq 0.05$$
$$H_A: p_T < 0.05,$$

where  $p_T$  is the probability of a Grade 3 or higher SLF across all study visits for Test lens. Based on Bayesian posterior probability distribution of the proportion  $p_T$ , superiority is interpreted as 95% probability of Test being statistically lower than the threshold of 5% (i.e.,  $p_T < 0.05$ ). If the upper bound of the 95% central posterior credible interval is below 0.05, it can be concluded that there is 95% probability that the Test lens is superior to 5% (statistically less than) based on the observed sample.

In the case of zero clinically significant SLF, a Bayesian hierarchical model accounting for zero event problem will be considered.

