### ***Unacceptable Lens Fitting***

Lens fit acceptance will be analyzed using a Bayesian beta-binomial model with correlated binary data.

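### The augmented density printed for the safety model contradicts the mixture stated above it; if that density is what is programmed, events in one eye only can wrongly fail a co-primary safety test

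*Combined protocol and SAP*

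**What the plan says.** All of this is in the protocol, section 14.5 (Primary Analysis), under The Model. For a subject's two-eye sum Y, the plan mixes Bin(2, p), with weight 1−ρ, and a modified Bernoulli, with weight ρ, described as "taking value 0 and 2 rather than conventional 0 and 1". The indicator set {0, 2} is printed with it. That mixture is a proper distribution.

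The text then brings in a device: "To overcome the complexity of the mixture likelihood a latent variable" Z, which equals 1 when the observation comes from the modified Bernoulli component. Under "The joint distribution of the augmented data" it prints a product in which that component appears as "p^{y_i z_i / 2} (1 - p)^{(2 - y_i) z_i / 2". The product carries no indicator on {0, 2}, and the binomial coefficient C(2, y) is not raised to the power 1−z. The index i is said to run over 1, 2.

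Estimation is by "The Metropolis sampler algorithm as implemented in the SAS/STAT MCMC Procedure". The decision rule for each safety hypothesis is "If the upper bound of the 95% central posterior credible interval is below 0.05". The second safety endpoint uses the same model: "Lens fit acceptance will be analyzed using a Bayesian beta-binomial model with correlated binary data". Section 14.6 names it again for the number of lenses needed.

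**The concern.** The two likelihoods in The Model are not the same, and the second is not a probability distribution. An event in one eye only is direct evidence that the eyes disagree. The printed joint density nevertheless lets it be credited to the component in which the eyes always agree. That pushes ρ towards 1, reduces the effective number of independent eyes and can raise the upper credible bound for p.

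Both safety hypotheses must be met before any efficacy hypothesis is tested (sections 2.3 and 14.4). With few events expected, the decision turns on individual event patterns close to the 5% limit. If the choice between the two likelihoods is left until data are seen, a primary decision could depend on it.

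**Working it through.** **Inputs.** From section 14.5: the mixture, the joint density, priors N(0, 1000) on β0 and β1 and Beta(0.5, 0.5) on ρ, and the pass rule (97.5th posterior percentile of p below 0.05). From section 14.2: 100 completers, up to 120 enrolled, reference rate 2%, between-eye correlation 0.70, and historical rate 0.24% (Table 7).

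**Assumptions.** 1000 is read as a variance. With one lens, logit(p) then has prior variance 1000 or 2000; both were tried, and also 1,000,000, with no change in the decisions at N=100. Zero events count as a pass. Posteriors were integrated on a grid. Write (a, b) for a subjects with an event in one eye and b with events in both.

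**1. The plan's own figure.** Table 8 gives 92.6% power per safety endpoint. At N=100, 2% and 0.70, the mixture gives 54.5% and the joint density 46.5%. Neither reproduces 92.6%. That is a separate question and is not used here.

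**2. Mass of the joint density.**

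| y | z=0 | z=1 as printed | z=1 required |
|---|---|---|---|
| 0 | (1−ρ)(1−p)² | ρ(1−p) | ρ(1−p) |
| 1 | 2(1−ρ)p(1−p) | 2ρ√(p(1−p)) | 0 |
| 2 | (1−ρ)p² | ρp | ρp |

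The total is 1 + 2ρ√(p(1−p)). At p=0.02, √(0.02×0.98)=0.14, so with ρ=0.7 it is 1 + 2×0.7×0.14 = 1.196. At p=0.05, ρ=0.7 it is 1.305. The excess depends on p and ρ, so it does not cancel as a constant, and summing over z does not return the mixture.

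**3. Where a one-eyed event goes.** P(z=1 | y=1) as printed is ρ/(ρ+(1−ρ)√(p(1−p))) = 0.7/(0.7+0.3×0.14) = 0.943. The mixture requires 0.

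**4. Upper 95% bounds at N=100.**

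| Pattern | Mixture | Joint density | Posterior mean of ρ |
|---|---|---|---|
| (4, 0) | 4.80% pass | 5.21% fail | 0.14 → 0.91 |
| (2, 1) | 4.97% pass | 5.16% fail | 0.46 → 0.90 |
| (0, 2) | 5.09% fail | 5.09% fail | unchanged |

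A coarser grid gives 4.78% to 5.19% for (4, 0) and 4.95% to 5.14% for (2, 1), so the second decimal depends on numerical settings. No other pattern changes at N=100.

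**5. Chance of passing one safety test, N=100, 2%, ρ=0.70.** Per subject, P(1)=2×0.3×0.02×0.98=0.01176 and P(2)=0.3×0.0004+0.7×0.02=0.01412. Multinomial probabilities are 7.45% for (2, 1) and 0.61% for (4, 0). So 54.51% − 7.45% − 0.61% ≈ 46.5%. At a 0.24% rate the two patterns together have probability of about 0.13%.

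**6. Dependence on N.** The analysis set is the safety population, not the completers.

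| N | Patterns that change | Loss at 2%, ρ=0.70 |
|---|---|---|
| 100 | (4, 0), (2, 1) | 8.1 points |
| 105 | none | 0 |
| 110 | at most (5, 0), whose mixture bound is 5.00% to two decimals | 0 to 0.2 |
| 115 | (5, 0), (3, 1) | 3.7 |
| 118 | (5, 0), (3, 1), (1, 2) | 13 |
| 120 | (5, 0): 4.61% to 5.05%; on a finer grid also (3, 1): 4.77% to 5.02% | 0.2 to 3.8 |

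Every change found was from pass to fail.

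**7. A partial repair does not work.** Raising C(2, y) to the power 1−z without the indicator still gives 5.22% for (4, 0) and 5.16% for (2, 1). The missing restriction is what matters.

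**The case against.** The best defence is that The Model supplies the restriction itself. It limits the modified Bernoulli to 0 and 2 and defines z=1 as membership of that component, so a careful reader would set z=0 whenever y=1 and treat the omission as notational. The list of parameters to be sampled is β0, β1 and ρ, without Z, which is compatible with coding the mixture directly. Section 14.1 leaves further detail to a stand-alone SAP. All of this stands: the documents do not say which form will be run. But the plan introduces the augmented form precisely to avoid the mixture likelihood and names the sampler soon after, so a programmer could reasonably code the joint density as printed.

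The size can also be challenged, and largely rightly. The 2% rate is the plan's own worst case. At 0.24% and ρ=0.70, about 73% of trials with N=100 would have no events, and a separate zero-event model is then to be considered. Most of the loss at N=100 comes from (2, 1), which passes so narrowly under the mixture that Monte Carlo error could decide it. Nor is the bound raised everywhere: with a single one-eyed event at N=120 it falls slightly (1.89% to 1.79%), far from the limit.

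The index i = 1, 2 is a slip with no numerical effect once one term per subject is coded.

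**Conclusion.** The contradiction is certain: it is algebra within one subsection and needs no assumption. The joint density exceeds total mass 1 whenever ρ>0 and 0<p<1. Its effect on the trial is conditional on that density being programmed. The loss in the chance of passing one safety test at 2% and ρ=0.70 then runs from 0 to about 13 points over the sizes checked (8.1 points at N=100), and is about 0.1% at the historical rate with N=100.

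A reader might infer more than this, without support from the documents:
- That the safety tests will be run on an invalid likelihood. The valid mixture is also printed, and coding it removes the problem.
- That an unsafe lens could pass. In the cases checked the error only turned passes into fails, so the risk is of wrongly failing the safety step and thereby blocking the efficacy tests.
- That 54.5% to 46.5% is a fixed cost. It belongs to N=100 and shifts with the final safety population.
- That this explains the 92.6% in Table 8. Neither likelihood reproduces that figure, and nothing shows which one the sizing simulation used.

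Should-fix.

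**What to change.** Do one of the following before database lock, in the protocol or the stand-alone SAP:
- Correct the joint density by forcing z_i=0 when y_i=1 and raising C(2, y_i) to the power 1−z_i.
- Preferably, drop Z and state that the mixture is coded directly: P(0)=(1−ρ)(1−p)²+ρ(1−p); P(1)=2(1−ρ)p(1−p); P(2)=(1−ρ)p²+ρp. These sum to 1.

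In either case, index i over subjects 1 to n. Use the same likelihood for both safety endpoints and, where the model is reused, for lens-fit success. Confirm that the sizing simulation used it, and rerun the simulation if it did not. The cost is one formula and a few lines of PROC MCMC code, plus a rerun at most; nothing changes at the sites.

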### Primary Safety Endpoint Sample Size Calculations:

#### Grade 3 or Higher Slit Lamp Findings (SLF) and Unacceptable Lens Fitting

Sample size estimates for SLFs grade 3 or higher and unacceptable lens fitting were calculated using the same technique and assumptions. Since both safety endpoints are testing against a 5% threshold and have an event rate less than 0.5% both endpoints require the same sample to achieve the same pre-specified confidence level of 95%. Furthermore, it should be noted that why both endpoints are collected on all subjects they are clinically independent.

For Grade 3 or Higher SLF was converted to a binary response as  $Y = 1$  if a subject eye has a clinically significant SLF and  $Y = 0$  otherwise for analysis purpose (Unacceptable lens fitting is derived as a binary response as  $Y=1$  is a subject had an unacceptable lens fit and 0 otherwise). From the historical data there was no/extremely low rate ( $< 1\%$ ) for clinically significant SLFs (Grade 3 or higher) or unacceptable lens fitting for the study lens. Assuming a correlation of 0.70 between left and right eyes within the same subject, a total of 2000 replicating trials were simulated with a reference rate of 2% (worse-case scenario). Given the rare event binary outcome of slit lamp findings, (or unacceptable lens fit) each replicated sample was analyzed using a Bayesian beta-binomial model with correlated binary data (Diniza et al; 2010). For each simulated trial, the upper bound of the 95% central posterior credible interval constructed for the percentage of Grade 3 or higher SLFs for the Test lens was compared to a margin of 5%. With the proposed sample size, there was at least 90% of the estimated 95% credible intervals with the upper bound being below 5%.

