# Clinical Study Protocol

## Johnson & Johnson Vision Care, Inc.

Endpoint Type	Endpoint	Test Type	Sample Size	Power (%)
Primary Safety	Grade 3 + SLF	Statistically less than (5%)	100	92.6
	Unacceptable Lens fitting	Statistically less than (5%)	100	92.6
Secondary	CLUE Vision-Hyperopes	Superiority (41)	16	82.4
	CLUE Vision Myopes	Superiority (46)	15	82.3
	CLUE Comfort (Hyperopes + Myopes)	Superiority (52)	11	83.8
	CLUE Handling (Hyperopes + Myopes)	Superiority (53)	17	83.7
	Lens Fit Success	Superiority (90%)	92	82.1

Based on the table above a total of at least 100 subjects a required to complete the study. To account for screen failures and subject dropout Up to 120 subjects (72 myopes and 48 hyperopes) will be enrolled to ensure at least 100 (60 myopes and 40 hyperopes) complete the study.

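### The safety model's "to be independent with a non-informative prior" is U-shaped on the event rate: at the planning assumptions a lens at exactly the 5% limit passes in 6.4% of trials, and the zero-event model is left open

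*Combined protocol and SAP*

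**What the plan says.** Section 14.5, under The Model, uses a mixture for the two eyes of a subject: with probability ρ the eyes share one outcome, otherwise they are independent. The logit of p is β0 + β1·lens. The coefficients are assumed "to be independent with a non-informative prior", N(0,1000), and ρ has a Beta(0.5, 0.5) prior. Lens fit is to be analysed with the same type of model.

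The rule is the same for both safety hypotheses: "If the upper bound of the 95% central posterior credible interval is below 0.05", the lens passes. Sections 2.3 and 14.4 require both to pass before efficacy is tested. No frequentist error rate is given for either.

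For zero events, Primary Safety Hypothesis 1 says that "a Bayesian hierarchical model accounting for zero event problem will be considered" and cites a paper. Hypothesis 2 says the same and defers details to the stand-alone SAP, which section 14.1 says will be final before database lock.

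Section 14.2 sets the planning case: a 2% event rate, "Assuming a correlation of 0.70 between left and right eyes within the same subject", and 100 completers, with enrolment up to 120. Table 7 gives historical rates of 0.24% (slit lamp findings, 1 eye) and 0% (unacceptable fit). Table 8 states 92.6% power for each endpoint.

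**The concern.** A normal prior with a very large variance looks harmless on the logit scale, but almost all of its mass maps to probabilities next to 0 or 1. With a rare event and a bound compared with 5%, that shape can decide borderline cases. These two endpoints are the eye-health and fit requirements and they open the efficacy testing. A reader would take the 95% central interval as about 2.5% protection against passing a lens at the limit. The plan does not say whether its model delivers that.

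The second question is what happens at zero events. That is the likeliest count at the historical rates, and there the plan points to a different model without committing to it.

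**Working it through.** **Inputs.** Prior, mixture and rule from section 14.5; n = 100, ρ = 0.70, margin 5% and planning rate 2% from section 14.2. N(0,1000) is read as variance 1000 (SD 31.6). In a single-arm trial β0 and β1 cannot be separated, so the variance on logit(p) could be 2000; the 6.4% below is unchanged with that, or with SD 1000. The Model defines p as acceptable fit. Prior and mixture are symmetric, so applying them to the event probability changes nothing.

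**Method.** Per subject, P(one eye) = (1−ρ)·2p(1−p) and P(both eyes) = (1−ρ)p² + ρp. At p = 5% and ρ = 0.7:
- one eye: 0.3 × 2 × 0.05 × 0.95 = 0.0285
- both eyes: 0.3 × 0.0025 + 0.7 × 0.05 = 0.03575
- neither: 0.93575

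The posterior was computed on a grid over logit(p) and ρ. A trial passes if P(p < 0.05 | data) ≥ 0.975, which is the upper limit of a 95% central interval. Pass probabilities are exact multinomial sums.

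**The plan's own figure.** Power at a 2% rate comes out at 54.5%, not 92.6%. No variant tried at n = 100 and 2% reaches 92.6%: one-sided 95% bound 62.2%, independent eyes 62.9%, both together 77.9%. At n = 120 power is 63.2%.

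**Prior on p.** logit(0.05) = −2.944, and −2.944/31.6 = −0.093, so P(p < 5%) = Φ(−0.093) = 46%. By symmetry P(p > 95%) = 46%, leaving 7% between. P(p < 0.1%) = Φ(−6.907/31.6) = 41%.

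**False pass at a true 5% rate, n = 100.**

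| ρ | N(0,1000) | Beta(0.5, 0.5) on p |
|---|---|---|
| 0 | 2.6% | 0.9% |
| 0.3 | 4.5% | 1.9% |
| 0.5 | 5.7% | 2.7% |
| 0.7 | 6.4% | 3.7% |
| 0.9 | 5.2% | 4.4% |

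Just above ρ = 0 the N(0,1000) figure is 2.7%. A simulation of 200,000 trials at ρ = 0.7 also gave 6.41%. A uniform prior on p gives 2.2% there. At n = 120 and ρ = 0.7, N(0,1000) gives 5.7%.

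The difference at ρ = 0.7 comes from two count patterns that pass only under N(0,1000):
- two subjects with one eye and one with both: posterior 0.9755, probability 485,100 × 0.0285² × 0.03575 × 0.93575^97 ≈ 2.2%
- four subjects with one eye: posterior 0.9804, probability 3,921,225 × 0.0285⁴ × 0.93575^96 ≈ 0.4%

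Together these are about 2.7 points, matching 6.41 − 3.73 = 2.68. With ρ held at 0.7 in the analysis, both priors give 4.1%, so part of the excess comes from estimating ρ.

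**Zero events.** P(zero) = [0.3(1−p)² + 0.7(1−p)]^100:
- p = 0.24%: 0.99688^100 = 73%
- p = 2%: 0.97412^100 = 7%

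The upper bound at zero events is 0.22% (variance 1000), 0.13% (variance 2000), 1.9% (Beta(0.5, 0.5)) or 2.9% (uniform). All are below 5%.

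**Power at ρ = 0.7, n = 100.**

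| True rate | N(0,1000) | Beta(0.5, 0.5) | Loss |
|---|---|---|---|
| 0.24% | 98.7% | 98.6% | 0.1 |
| 0.5% | 95.1% | 94.2% | 0.8 |
| 1% | 83.6% | 80.0% | 3.5 |
| 2% | 54.5% | 46.5% | 8.0 |

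Losses are taken before rounding.

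**The case against.** The criterion is Bayesian and the plan promises no frequentist error rate for these endpoints; section 14.4 allocates 5% only to the efficacy family. That stands: 2.5% is what a 97.5% bound implies, not a commitment that the plan breaks. The plan itself reads a pass as 95% probability. Against a 5% yardstick, 6.4% is only a little high and 3.7% is inside it.

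The 6.4% is also close to the worst case. It applies at the 5% boundary and falls to 2.6% at a true 6% and 1.0% at 7%. It depends on an assumed ρ. Both endpoints must pass, so opening the gate is no more likely than passing either one.

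Three stronger readings are tempting, and the documents do not support them.
- **The prior is tilted towards safety.** It is symmetric, with as much mass above 95% as below 5%. The pull appears only once data with few events rule out the upper half.
- **The model breaks down at zero events.** The posterior is proper and every prior checked passes. The plan foresees another model for that case.
- **The safety model will be picked after the result is known.** The trigger, the model class and a reference are written in advance, and the SAP is to be final before lock. The stand-alone SAP is not among the documents, so it may settle the details. What remains is that the model is only to be considered, and that the text for Hypothesis 1 does not defer to the SAP.

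Finally, Beta(0.5, 0.5) does not itself reach 2.5% at high ρ. That is correct.

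**Conclusion.** The point holds in limited form. The label non-informative is not earned on the scale that matters. At every ρ in the table the stated prior is more permissive than Beta(0.5, 0.5), and at the plan's n and ρ the false-pass rate at the limit is 6.4% rather than 3.7%. Part of this comes from estimating ρ, so the prior should not be charged with all of the excess over 2.5%.

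At zero events nothing turns on the prior for the decision. The reported bound, however, reflects the choice of prior scale more than the data, and the document does not commit to the model that would replace it. Zero is the likeliest count at the historical rates but not at the planning rate.

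These results assume the section 14.5 mixture, ρ = 0.70 unless varied, and 100 analysed subjects unless stated.

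**What to change.** In section 14.5 and the SAP, put p ~ Beta(0.5, 0.5) directly on the eye-level event probability and keep Beta(0.5, 0.5) for ρ. Use this one model for every count, zero included, for both safety hypotheses, and delete the zero-event fallback from both. Report the false-pass rate at a true 5% over a range of ρ beside the power.

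The cost is SAP wording, a rerun of the simulation and the power losses tabulated above: negligible at the historical rates, 3.5 points at 1% and about 8 points at 2%. The false-pass rate falls but stays above 2.5% from about ρ = 0.5 upwards, so it should be stated rather than assumed.

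The rerun must also restate the 92.6% in Table 8 and the combined power built on it. At a 2% rate the figure is about 54.5% under the stated prior and 46.5% under Beta(0.5, 0.5), both short of the 90% minimum in section 14.2. The planning rate or the sample size then needs its own justification.
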